## **9. STATISTICAL METHODOLOGY**

### **9.1 General**

Data listings will be provided for all data that is databased. Summary statistics and statistical analysis will only be presented for data where detailed in this SAP. For continuous data, summary statistics will include the arithmetic mean, arithmetic standard deviation (SD), median, minimum, maximum and n (number of subjects); for log-normal data (e.g. the PK parameters: AUCs and  $C_{max}$ ) the geometric mean and geometric coefficient of variation (CV%) will also be presented. For categorical data, frequency count and percentages will be presented. Data listings will be provided for all participants up to the point of withdrawal, with any participants excluded from the relevant population highlighted. Summary statistics and statistical analyses will generally only be performed for participants included in the relevant analysis population. For the calculation of summary statistics and statistical analysis, unrounded data will be used.

Mean change from baseline is the mean of all individual participants' change from baseline values. Each individual change from baseline will be calculated by subtracting the individual participant's baseline value from the value at the timepoint. The individual participant's change from baseline values will be used to calculate the mean change from baseline using a SAS procedure such as Proc Univariate.

Data analysis will be performed using SAS® Version 9.4 or greater.

### **9.2 Demographics and Participant Disposition**

Participant disposition will be summarized and listed. The demographic variables age, sex, race, ethnicity, country of enrolment, site ID, body weight, height and body mass index will be summarized and listed. All other demographic variables will be listed only.

### **9.3 Pharmacokinetic Assessment**

#### **9.3.1 Pharmacokinetic Analysis**

Noncompartmental methods applied with a validated software program (Phoenix WinNonlin Version 8.1 or later) to the plasma concentrations of selpercatinib will be used to determine the following PK parameters, when possible:

Parameter	Units	Definition
AUC(0-t last )	ng.h/mL	area under the concentration versus time curve from time zero to time t, where t is the last time point with a measurable concentration
AUC(0-∞)	ng.h/mL	area under the concentration versus time curve from time zero to infinity
C max	ng/mL	maximum observed drug concentration
t max	h	time of maximum observed drug concentration
t 1/2	h	half-life associated with the terminal rate constant ( $\lambda_z$ ) in non-compartmental analysis
CL/F	L/h	apparent total body clearance of drug calculated after extra-vascular administration
V Z/F	L	apparent volume of distribution during the terminal phase after extra-vascular administration
V ss/F	L	apparent volume of distribution at steady state after extra-vascular administration

Additional PK parameters may be calculated, as appropriate.

The software and version used for the final analyses will be specified in the CSR. Any exceptions or special handling of data will be clearly documented within the final CSR.

Formatting of tables, figures and abbreviations will follow the Eli Lilly Global PK/PD/TS Tool: NON-COMPARTMENTAL PHARMACOKINETIC STYLE GUIDE. The version of the tool effective at the time of PK analysis will be followed.

### General PK Parameter Rules

- Actual sampling times will be used in the final analyses of individual PK parameters, except for non-bolus pre-dose sampling times which will be set to zero.
- Cmax and tmax will be reported from observed values. If Cmax occurs at more than one time point, tmax will be assigned to the first occurrence of Cmax.
- AUC parameters will be calculated using a combination of the linear and logarithmic trapezoidal methods (linear-log trapezoidal rule). The linear trapezoidal method will be applied up to tmax and then the logarithmic trapezoidal method will be used after tmax. The minimum requirement for the calculation of AUC will be the inclusion of at least three consecutive plasma concentrations above the lower limit of quantification, with at least one of these concentrations following Cmax.
- The t1/2 will be calculated, when appropriate, based on the apparent terminal log-linear portion of the concentration-time curve. The start of the terminal elimination phase for each subject will be defined by visual inspection and generally will be the first point at which there is no systematic deviation from the log-linear decline in plasma concentrations. Half-life will only be calculated when a reliable estimate for this

parameter can be obtained comprising of at least 3 data points. If  $t_{1/2}$  is estimated over a time window of less than 2 half-lives, the values will be flagged in the data listings. Any  $t_{1/2}$  value excluded from summary statistics will be documented in the footnote of the summary table.

- A uniform weighting scheme will be used in the regression analysis of the terminal log-linear portion of the concentration-time curve.
- The parameters based on last predicted observed drug concentration ( $C_{last}$ ) will be reported (except in bioequivalence and bioavailability studies, where only the observed parameters will be reported).

### **Individual PK Parameter Rules**

- Only quantifiable concentrations will be used to calculate PK Parameters with the exception of special handling of certain concentrations reported below the lower limit of quantitation (BQL). Plasma concentrations reported as BQL will be set to a value of zero when all of the following conditions are met:
  - The compound is non-endogenous.
  - The samples are from the initial dose period for a subject or from a subsequent dose period following a suitable wash-out period.
  - The time points occur before the first quantifiable concentration.
- All other BQL concentrations that do not meet the above criteria will be set to missing.
- Also, where two or more consecutive concentrations are BQL towards the end of a profile, the profile will be deemed to have terminated and therefore any further quantifiable concentrations will be set to missing for the calculation of the PK parameters unless it is considered to be a true characteristic of the profile of the drug.

### **Individual Concentration vs. Time Profiles**

- Individual concentrations will be plotted utilizing actual sampling times.
- The terminal point selections will be indicated on a semi-logarithmic plot.

### **Average Concentration vs. Time Profiles**

- The average concentration profiles will be graphed using scheduled (nominal) sampling times.
- The average concentration profiles will be graphed using arithmetic average concentrations.

- The pre-dose average concentration for single-dose data from non-endogenous compounds will be set to zero. Otherwise, only quantifiable concentrations will be used to calculate average concentrations.
- Concentrations at a sampling time exceeding the sampling time window specified in the protocol, or  $\pm 10\%$ , will be excluded from the average concentration profiles.
- Concentrations excluded from the mean calculation will be documented in the final CSR.
- A concentration average will be plotted for a given sampling time only if 2/3 of the individual data at the time point have quantifiable measurements that are within the sampling time window specified in the protocol or  $\pm 10\%$ . An average concentration estimated with less than 2/3 but more than 3 data points may be displayed on the mean concentration plot if determined to be appropriate and will be documented within the final CSR.

### **Treatment of Outliers during Pharmacokinetic Analysis**

Application of this procedure to all PK analyses is not a requirement. Rather, this procedure provides justification for exclusion of data when scientifically appropriate. This procedure describes the methodology for identifying an individual value as an outlier for potential exclusion, but does not require that the value be excluded from analysis. The following methodology will not be used to exclude complete profiles from analysis.

#### Data within an Individual Profile

A value within an individual profile may be excluded from analysis if any of the following criteria are met:

- For PK profiles during multiple dosing, the concentration of the pre-dose sample exceeds all measured concentrations for that individual in the subsequent post-dose samples.
- For PK profiles during single dosing of non-endogenous compounds, the concentration in a pre-dose sample is quantifiable.
- For any questionable datum that does not satisfy the above criteria, the profile will be evaluated and results reported with and without the suspected datum.

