2.2. Background

Selpercatinib (LY3527723) is a highly potent and specific small-molecule inhibitor of the RET kinase, with minimal inhibition of other kinase and nonkinase targets.

Selpercatinib doses have been evaluated in healthy participants and patients with advanced or metastatic RET-mutant MTC, advanced or metastatic RET fusion-positive thyroid cancer, other RET fusion-positive solid tumors, and metastatic RET fusion-positive NSCLC across Phase 1, 2, and 3 clinical studies. Across these studies, single oral doses of selpercatinib were administered over a range of 20 to 720 mg. Multiple oral doses of 160 mg/day selpercatinib were administered orally twice daily for 10 days in healthy volunteers. Pediatric dose was selected to be 92 mg/m^2 , (maximum 160 mg BID).

The pharmacokinetics of selpercatinib is characterized by good oral bioavailability, with a t_{max} of approximately 2 hours (range 0 to 8.1 hours). CYP3A4 mediated metabolism constitutes the major route of elimination, and the $t_{\frac{1}{2}}$ is approximately 32 hours in healthy volunteers. The $V_{\text{ss/F}}$ and CL/F of selpercatinib increased with increasing body weight (27 kg to 177 kg). No clinically significant differences in the PK of selpercatinib were observed based on age (15 years to 90 years), or sex. As the PK of selpercatinib have been demonstrated to be linear in the dose range of 20 to 160 mg in adult cancer patients, results from study JZJU can be expected to be applicable across the therapeutic dose range.

More detailed information about the pharmacokinetics (PK) and absorption, distribution, metabolism, and excretion properties of selpercatinib may be found in the IB.

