**Figure 2: Treatment Sequences for Study J2G-MC-JZJU**

There will be a washout of 7 days between doses of selpercatinib. Participants will remain resident at the CRU for the full duration of the treatment period (i.e., up to Day 21).

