## 7. SAMPLE SIZE JUSTIFICATION

Up to approximately 42 participants will be enrolled to ensure that at least approximately 36 participants complete the study. The sample size for this study is justified based on a precision for the ratio of geometric means and it is represented by the half-width of the 90% confidence interval (CI) of the point estimate on the logarithmic scale. Based on an intra-participant variability of 70% (LOXO-RET-19075), with a probability of 90%, a 90% CI for the ratio of the geometric means for  $C_{max}$  and area under the concentration versus time curve (AUC) will be obtained with a precision about 0.288 in the log scale, which corresponds to approximately 0.334 in the natural scale.

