#### Reporting of Excluded Values

Individual values excluded as outliers will be documented in the final CSR. Approval of the final CSR will connote approval of the exclusion.

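### Does allowing quantifiable pre-dose values in Periods 2 and 3 to be dropped as outliers distort the bioavailability ratios?

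*SAP*

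**What the plan says.** The outlier part of SAP 9.3.1 allows, but does not oblige, the analyst to drop a value from an individual profile on either of two grounds. The one that matters for a single-dose study is "For PK profiles during single dosing of non-endogenous compounds, the concentration in a pre-dose sample is quantifiable". It carries no limit by period and no threshold relative to Cmax. A doubtful value that meets neither ground must have "results reported with and without the suspected datum"; a quantifiable pre-dose value meets one, so that duty does not reach it.

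Three other rules in SAP 9.3.1 bear on the point:

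- For values below the quantitation limit, Individual PK Parameter Rules separates the first period from later ones: "The samples are from the initial dose period for a subject or from a subsequent dose period following a suitable wash-out period". It does not define a suitable washout.
- For mean plots, "The pre-dose average concentration for single-dose data from non-endogenous compounds will be set to zero".
- "Individual values excluded as outliers will be documented in the final CSR".

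On design, "There will be a washout of 7 days between doses of selpercatinib", and Protocol 2.2 says the half-life "is approximately 32 hours in healthy volunteers". The primary model in SAP 9.3.2 has formulation, period, sequence and participant, with no carryover term in the visible text. A blacked-out block follows it, before the tmax analysis.

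**The concern.** A pre-dose value means different things in different periods. Before any dosing, a quantifiable concentration of a drug the body does not make points to a sample or assay fault, and an outlier rule is the right place for it. Seven days after a dose of a drug with a 32 h half-life, it is what the kinetics predict. The SAP treats both alike and calls both potential outliers.

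The remedy also looks misdirected. Residual drug sits under the whole of the next profile, so deleting the time-zero value leaves it in every later concentration and hence in AUC and Cmax, the primary parameters. The visible text provides no corrected analysis, and the mean plot would show zero whatever was measured. If the residual depends on which formulation came before, it could bias the RTU/capsule and PFOS/capsule ratios while the only named action leaves that bias in place.

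**Working it through.** **Inputs.** Doses 168 h apart (Days 1, 8 and 15); half-life about 32 h and tmax about 2 h (Protocol 2.2); intra-participant CV 70%, 36 completers and half-width 0.288 (SAP 7). Assumed, because the visible text does not give them: first sample at 0.5 h, last at 144 h, the sequences, and the true formulation ratios.

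**1. The plan's own precision.** σ_w = √ln(1 + 0.70²) = 0.6315. Half-width with 90% probability = t(0.95, df) × σ_w × √(2/36) × √(χ²(0.90, df)/df). With df = 34: 1.691 × 0.6315 × 0.2357 × √(44.90/34) = 0.289, against the stated 0.288. With the 68 to 70 df of a three-period model it is about 0.274 to 0.275. Either serves as the yardstick; exp(0.288) − 1 = 0.334.

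**2. Residual.** 168/32 = 5.25 half-lives; r = 2^(−5.25) = 0.0263. In a one-compartment oral model the pre-dose value is about 2.77% of the previous Cmax.

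**3. What excluding the point does.** The SAP's trapezoidal rule (linear up to tmax, logarithmic after) on that model, with equal exposure in both periods, gives:

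| Period 2 handling | Change in AUC(0-tlast) | Change in Cmax |
|---|---|---|
| as observed | +2.66% | +2.65% |
| pre-dose value removed (zero at time 0) | +2.64% | +2.65% |
| C0·exp(−λz·t) subtracted | 0.00% | 0.00% |

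By hand: removal takes out a triangle of ½ × 0.5 h × 0.0277 Cmax = 0.0069 Cmax·h, from an AUC of about 46 Cmax·h. That is 0.015%.

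**4. What reaches the ratios.** Fit the SAP's fixed effects to log(F_current + r·F_previous + r²·F_first), where the last term applies in Period 3. Carryover common to all formulations goes into the period effect. Only the part that depends on the preceding formulation is left.

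Example: RTU at 0.7, capsule and PFOS at 1, sequences capsule–PFOS–RTU, PFOS–RTU–capsule and RTU–capsule–PFOS.

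- RTU, mean log excess: [0 + ln(1 + 0.0263/0.7) + ln(1 + 0.0270/0.7)]/3 = (0 + 0.0369 + 0.0378)/3 = 0.0249.
- Capsule: [0 + ln(1 + 0.0184) + ln(1 + 0.0191)]/3 = (0 + 0.0182 + 0.0189)/3 = 0.0124.
- Difference 0.0125, a bias of +1.26%.

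Over both period-balanced three-sequence squares:

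| True ratios to capsule | Bias in that suspension's ratio |
|---|---|
| both 1 | 0 |
| one at 0.7, other 1 | +0.75% or +1.26% |
| one at 1.25, other 1 | −0.35% or −0.77% |
| 0.7 and 1.25 | at most 1.86% in size |

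On the log scale 1.86% is 0.0184, which is 0.0184/0.288 = 6.4% of the planned half-width.

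**5. With random variation.** A simulation of 40,000 participants per sequence used 70% CV, an assumed 25% CV in half-life and 10% assay error. AUC(0-tlast) bias, as observed and then after deleting pre-dose values: 1.25/1.25% and 2.20/2.19% (one suspension at 0.7), −0.65/−0.65% and −1.36/−1.36% (one at 1.25). Deletion makes no practical difference. Subtraction brings AUC within 0.03% and Cmax within 0.31%.

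**6. Wider assumptions.** With the suspensions at 1.5 and 0.67, the 32 h bias reaches about 3.8% with random variation. At an assumed 50 h half-life it is 1.7 to 6.0% in AUC for one suspension at 0.7 or 1.25. At an assumed 48 h with 1.5 and 0.67 it reaches about 11%. In the other direction, if only 0.3 of Cmax belongs to the terminal phase (assumed 6 h distribution half-life), the rises in step 3 fall to about 0.9% for Cmax and 1.8% for AUC.

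**The case for a change.** The strongest case for a change is that the rule is wrong in kind for two of three periods, and that a better handling costs little: SAP wording, one table of pre-dose values as a percentage of Cmax, and one residual-subtracted run. Means also hide individuals. If the 70% CV applies independently to each period, the residual relative to the current profile has a median of 2.6% but a 95th percentile of 11.4%. The bias grows with half-life and with formulation differences, and those differences are what the study sets out to measure. Documenting exclusions in the CSR happens after results are known.

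Part of this stands. The criterion does not distinguish periods, a table of pre-dose values would be informative, and subtraction removes nearly all of the bias in the model used. That last result partly reflects the model, since single-exponential subtraction is correct there by construction; in real data it needs a rule for which λz to use and what to do when half-life cannot be estimated.

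The case for a required change does not stand. Confining the exclusion to Period 1 would alter AUC by about 0.015% and leave Cmax as it is. The exemption from reporting both ways is equally empty, since the two results would agree to that margin. The plotted mean enters no primary analysis. Large residuals in individuals do not by themselves bias the ratio: with equal exposures and the full 70% variability, the calculated bias was within 0.01%.

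**Conclusion.** No change to the plan is needed. The observation is correct, but the exclusion rule neither creates nor removes the carryover bias. That bias comes from residual drug after the washout. At the documented half-life it is zero for equal exposures, 0.35 to 1.3% for one suspension at 0.7 or 1.25, and up to 1.9% for both. With random variation the single-suspension figure is 0.65 to 2.2%. Against this, the CI "will be obtained with a precision about 0.288 in the log scale". The visible text sets no equivalence limits that a shift of this size could decide.

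The rule is also hedged. SAP 9.3.1 requires no exclusion, offers it only where there is scientific reason, forbids using the procedure to discard whole profiles, and requires excluded values to be reported. An analyst who sees a Period 2 value in line with ordinary washout has no cause to remove it, and little changes if it is removed.

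This rests on assumed formulation ratios, period-balanced sequences and one-compartment kinetics at about 32 h. The 11% figure needs a half-life and formulation differences that the documents do not suggest. Two things cannot be settled from the public text: whether residuals will be quantifiable at all after 20 mg, and whether the blacked-out part of SAP 9.3.2 already holds a sensitivity analysis. Tabulating the Period 2 and 3 pre-dose values is a reasonable courtesy in the CSR, but sound results do not depend on it.

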#### Data between Individual Profiles

1. If  $n < 6$ , then the dataset is too small to conduct a reliable range test. Data will be analyzed with and without the atypical value, and both sets of results will be reported.
2. If  $n \geq 6$ , then an objective outlier test will be used to compare the atypical value to other values included in that calculation:
  - a. Transform all values in the calculation to the logarithmic domain.

- b. Find the most extreme value from the arithmetic mean of the log transformed values and exclude that value from the dataset.
- c. Calculate the lower and upper bounds of the range defined by the arithmetic mean  $\pm 3 \times \text{SD}$  of the remaining log-transformed values.
- d. If the extreme value is within the range of arithmetic mean  $\pm 3 \times \text{SD}$ , then it is not an outlier and will be retained in the dataset.
- e. If the extreme value is outside the range of arithmetic mean  $\pm 3 \times \text{SD}$ , then it is an outlier and will be excluded from analysis.

If the remaining dataset contains another atypical datum suspected to be an outlier and  $n \geq 6$  following the exclusion, then repeat step 2 above. This evaluation may be repeated as many times as necessary, excluding only one suspected outlier in each iteration, until all data remaining in the dataset fall within the range of arithmetic mean  $\pm 3 \times \text{SD}$  of the log-transformed values.

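### The optional 3-SD outlier rule can be read to drop valid Cmax and AUC values, and no visible text requires the result with those values kept

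*SAP*

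**What the plan says.** SAP 9.3.1, under Treatment of Outliers during Pharmacokinetic Analysis, makes the procedure optional. It states that "this procedure provides justification for exclusion of data when scientifically appropriate", that it identifies candidates "but does not require that the value be excluded from analysis", and that "The following methodology will not be used to exclude complete profiles from analysis".

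The subsection Data between Individual Profiles then splits by sample size:

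- **Fewer than six values:** "Data will be analyzed with and without the atypical value, and both sets of results will be reported".
- **Six or more values:** "an objective outlier test will be used to compare the atypical value to other values included in that calculation". Values are log-transformed, the most extreme is set aside, and it is compared with the mean plus or minus 3 SD of the rest. If it lies outside, "then it is an outlier and will be excluded from analysis". "This evaluation may be repeated as many times as necessary, excluding only one suspected outlier in each iteration".

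For a questionable point inside one participant's profile, the subsection Data within an Individual Profile asks that "the profile will be evaluated and results reported with and without the suspected datum".

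Excluded values are documented in the clinical study report, and approval of that report counts as approval of the exclusion (Reporting of Excluded Values). The visible text of SAP 9.3.2, which defines the primary mixed model for log Cmax and the two AUCs, names no sensitivity analysis. Part of that section is redacted.

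**The concern.** With 36 to 42 participants the six-or-more branch governs this study. That branch removes a value for being extreme, without any identified error. It does not name Cmax or AUC, but its position in the PK analysis section, its log transform, its between-participant comparison and its open reference to the values in a calculation all allow it to be applied to them.

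Three things are left open:

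- **Timing.** Nothing visible says when the decision to invoke the test is made. In an open-label study it can be made with results by formulation in view.
- **Paired results.** The SAP asks for results with and without the value in two neighbouring situations, but not in the branch that applies here.
- **Scope of the complete-profile bar.** It is not said whether dropping a participant's Cmax and AUC for one period counts as excluding a complete profile.

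The preamble, where exclusion is not required, and the final step, where the value will be excluded, also need to be reconciled. What is at stake is the reported ratio and its 90% CI. No pass/fail limit is visible, so no decision threshold is shown to be crossed.

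**Working it through.** **1. The plan's precision figure reproduces.** Inputs are from SAP 7: within-participant CV 70%, 36 completers, 90% CI, 90% assurance.

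- Log SD = sqrt(ln(1 + 0.70²)) = 0.6315.
- Half-width = t(0.95, 35) × 0.6315 × sqrt(2/36) = 0.2515. Multiplying by sqrt(chi²(0.90, 35)/35) gives 0.2885, against the stated 0.288.
- exp(0.288) − 1 = 0.334, as stated.

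The average half-widths in step 3 are lower because they carry no assurance factor and use about 68 df; the same formula with 68 df and no assurance factor gives 0.248.

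**2. How often the rule fires on clean data.** For a log-normal value among n, the chance of lying outside the leave-one-out 3-SD range is 2 × P(t(n−2) > 3/sqrt(1 + 1/(n−1))).

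- At n = 36 this is 0.0056 per value. Simulating the repeated test gives at least one flag in 20.2% of calculations (20.7% at n = 42).
- Two formulations: 1 − (1 − 0.202)² = 36%. Three: 1 − (1 − 0.202)³ = 49%.
- With participants' values correlated across periods, the simulated three-formulation figure is 47-49%.

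**3. Effect on the primary model.** Assumptions: a balanced three-sequence Latin square (the sequence figure is not shown), 36 participants, between-participant log SD 0.2/0.4/0.6, true ratio 1, test always applied. Each setting used 4000 trials, fitted by REML with the SAP 9.3.2 effects.

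| Errors | Data used | Half-width | Coverage (%) |
|---|---|---|---|
| Normal | All values | 0.2458 / 0.2473 / 0.2474 | 90.5 / 90.6 / 90.7 |
| Normal | After rule | 0.2408 / 0.2440 / 0.2455 | 89.1 / 89.6 / 89.8 |
| t(4), same variance | All values | 0.2433 / 0.2446 / 0.2447 | 89.5 / 89.6 / 89.6 |
| t(4), same variance | After rule | 0.2069 / 0.2160 / 0.2233 | 86.4 / 87.3 / 88.1 |

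- **Normal errors:** the CI is 1-2% narrower (0.2408/0.2458 = 0.980; 0.2455/0.2474 = 0.992), coverage drops 0.9-1.4 points and the ratio is unbiased. In affected suspension/capsule pairs the ratio moves by a median of 0.05 log (90th percentile 0.09).
- **t(4) errors:** the CI is 9-15% narrower (0.2069/0.2433 = 0.850; 0.2233/0.2447 = 0.913) and coverage drops 1.5-3.1 points.

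A separate set of 3000 trials per setting looked only at trials that lost a value. On normal errors, coverage there went from 90-91% to 86-87%. A fall of 3.4-4.0 points in 47-48% of trials is 1.6-1.9 points overall, so about 1-2 points is a fair summary of both sets.

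**4. Selective use.** If only flagged low suspension values and flagged high capsule values are dropped, the mean ratio (true 1.00) becomes 1.013/1.013/1.012 on normal data and 1.057/1.045/1.033 on t(4) data. The mirror choice moves it the other way.

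**5. Does the complete-profile bar prevent this?** With Cmax-AUC log correlation assumed at 0.5/0.7/0.9 and between-participant SD 0.4, the share of flagged doses flagged on only one of the two parameters is 97/91/72% on normal data and 87/78/58% on t(4) data. Dropping that one value does not drop a complete profile.

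The bar matters more for a grossly low dose. One suspension dose in 36 at 5% of expected exposure shifts the log ratio by ln(0.05)/36 = −0.083, to 0.92, and exclusion returns it to 0.97-1.00. Such a dose is flagged on both parameters in 74-80% of trials, so the bar could stop much of that case.

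**The case against.** The strongest reply is that the reach to Cmax and AUC is inferred. The rule is in 9.3.1, not in the section that defines the primary model, and where the SAP removes participants from inference (vomiting, SAP 8) it says so. That is why the claim goes no further than that the rule can be read this way. The SAP should settle it.

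Other points carry weight:

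- Cmax is an observed concentration, so a Cmax that looks wrong within its own profile already gets results both ways. The gap concerns values that are extreme only across participants.
- The plan has real safeguards: SAP sign-off before the first visit, use limited by scientific judgement, full data listings, and documentation of special handling and exclusions. These disclose which value was dropped. None of the visible text requires its effect on the ratio to be shown.
- The redacted part of 9.3.2, or the table shells, may contain a sensitivity analysis. If so, a cross-reference would be enough for the paired result.
- The 47-49% rate assumes the test is always run, whereas the SAP runs it on a value suspected to be atypical. It is an upper-end figure for exclusions and does not measure bias.
- The larger effects need t(4) errors, and the 3-6% shift also needs one-directional use. The documents establish neither.
- The preamble and the final step can be read together, with the step operating inside an optional procedure. The wording still invites two readings.

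It can also be said that one sentence requiring paired results would close the gap. That would meet the minimum, but it leaves open which result is primary.

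**Conclusion.** The concern holds as a cheap improvement. At the sample size of this study, the SAP lets an optional and repeatable test remove values with no identified error, and no visible text requires the result with those values retained. Applied consistently to log-normal data, it does little harm: no bias, an interval 1-2% narrower, and about 1-2 points of coverage. The exposure comes from discretionary use and heavy tails, and even there the mean shift of 3-6% is small beside the planned precision of 0.288 log (about 33%). The sizes rest on an assumed balanced Latin square, assumed between-participant SDs of 0.2-0.6 and the assumed error shapes. The reading of the text depends on none of these, but it is limited to unredacted text.

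**What to change.** In SAP 9.3.1 and 9.3.2:

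- State that the primary mixed model uses all evaluable Cmax, AUC(0-∞) and AUC(0-tlast) values.
- Allow exclusion only for documented assay, dosing or sampling errors, or under exclusions the SAP already specifies (such as vomiting, SAP 8), decided before results by formulation are reviewed.
- Use the 3-SD test only as a flag. Whenever it fires, report the outlier-excluded model as a sensitivity analysis, which extends to six or more values the paired reporting already required elsewhere in 9.3.1.
- Say how the complete-profile sentence applies to derived parameters, and reconcile the optional preamble with the final exclusion step.

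The cost is SAP wording and one further run of the same model if a value is flagged. Sample size and stated precision do not change. The primary CI would be slightly wider than under the rule: 1-2% on clean log-normal data, and about 10-18% under t(4) errors (0.2447/0.2233 = 1.10; 0.2433/0.2069 = 1.18), where the narrower interval covers only 86-88%.
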